1.1 Background and rationale

The majority of injuries in Norwegian youth occur in a sports setting (1). Sports injuries are a significant public burden in terms of healthcare costs and place the individual youth at higher risk of developing subsequent health problems (2, 3). Additionally, sports-active youth often reduce or altogether cease their engagement in sports and physical activities following injury (4). The down-stream consequences of injuries sustained during sports should therefore not be underestimated. Handball and football are the most popular sports among Norwegian youth. The combination of the high physical demands inherent to these sports and the ongoing process of growth and maturation makes youth handball and football players notably susceptible to injury (5-7). Common injuries observed among youth who play handball and football encompass muscular and ligamentous ruptures, bone stress injuries, and injuries to the growing physes (5, 8).

Several injury prevention programs are effective in reducing injury occurrences. Soligard, Myklebust (9) showed a reduction in injuries overall, overuse injuries, and severe injuries in youth female football by implementing the FIFA 11+ injury prevention program. This multicomponent program, which targets both neuromuscular control and muscle strength, was subsequently adapted for specific populations, such as FIFA 11+ Kids (10) and a tailored shoulder injury prevention program for goalkeepers (11). Other efficacious injury prevention programs targeting specific injuries include the Nordic Hamstring for hamstring muscle ruptures (12) and Copenhagen Adductor Exercise for adductor muscle ruptures (13). In handball, structured warm up programs have proven efficacious in preventing lower extremity injuries and shoulder injuries (14-16). However, the gap between efficacy trials and real-world implementation remains a significant challenge.

Against this backdrop, the #Utviklingsklar project commenced in 2021. It is a collaborative and knowledge-sharing project funded by the Research Council of Norway. The overall aim of the project is to develop and evaluate a new program, based on interdisciplinary program theory from sport sociology, biomedicine, and health behavior, to reduce first-time and recurrent injury in youth handball and football. The project follows the UK Medical Research Council (MRC) framework for developing complex health interventions (17). The MRC framework emphasizes the importance of research methods that focus not solely on efficacy, but also on the mechanistic workings of an intervention, and whether it can be implemented in a real-world setting (17).

During the first two years of the project, we undertook development and feasibility testing of the novel #Utviklingsklar intervention. *#Utviklingsklar* is a club-based intervention designed to improve injury-preventive coaching practices. By participating in the intervention, coaches and club leaders develop plans and practices for injury-preventive warm-ups, strength training, and management of players with current pain and injury. The program theory underpinning the intervention is based on previous research within this field, preliminary work conducted in the research project, public involvement, and established theoretical

STATISTICAL ANALYSIS PLAN for Effectiveness of the Injury-preventive Program #Utviklingsklar

frameworks. First, we conducted a comprehensive literature review to dissect the biomedical mechanisms underlying the effect of injury prevention programs in handball and football. This review culminated in the formulation of causal biomedical models informed by previous research. Second, a cross-sectional study on behavioral constructs using the Health Action Process Approach was conducted, garnering responses from 865 youth handball and football coaches and players. Outcomes revealed a distinct need for increased knowledge, self-efficacy, and tools to aid coaches in managing pain and injuries in youth players. Third, a second literature review was conducted, focusing on the influence of sociocultural forces on injuries in the youth sport context. Critical to the developmental process was extensive knowledge exchange with the sporting community through meetings and discussion with project partners NIF, NHF, NFF, and key end users (club leaders, coaches, youth players, and their parents). Results from the preliminary work and feedback from stakeholders guided intervention development and content. The feasibility assessment, conducted with participation of three clubs from youth handball and football, prompted minor program revisions and indicated that a large-scale evaluation was warranted.

The current statistical analysis plan describes the evaluation of #Utviklingsklar in handball. The project is embedded within the context of Norwegian youth sport. Findings from this evaluation will guide future initiatives to protect youth health among project partners NIF, NHF and NFF. It is therefore of primary interest to investigate how injuries are affected by the #Utviklingsklar program compared to usual practice, which may or may not involve other initiatives to prevent injury.

Central to the evaluation is the hypothesis that injuries in the youth sporting context are influenced by injury-preventive coaching practices. These practices encompass injury-preventive warm-ups, injury-preventive strength training, and management of players with pain and injury, including adjusting training and match loads and guiding youth towards appropriate medical care when necessary. Moreover, these coaching practices are hypothesized to be influenced by specific behavioral determinants, alongside the broader sociocultural context and interpersonal dynamics inherent in the youth sport setting. The current evaluation aims not only to produce knowledge on how injuries are affected by the implemented intervention, but also how injuries are affected by factors in the proposed causal pathway, as outlined in the program theory.

1.2 Trial Objectives

1.2.1 Primary Objective

The primary objective is to compare the effectiveness of #Utviklingsklar to usual practice on the weekly injury severity score in youth handball players over one season.

1.2.2 Secondary Objectives

The secondary objectives are:

- To compare the effectiveness of #Utviklingsklar versus usual practice on injury consequences in youth handball players over one season.

STATISTICAL ANALYSIS PLAN for Effectiveness of the Injury-preventive Program #Utviklingsklar

- To compare the effectiveness of #Utviklingsklar versus usual practice on handball youth coaches' determinants of injury-preventive behavior at mid-season and end of season.
- To compare the effectiveness of #Utviklingsklar versus usual practice on injury-preventive coaching practice among youth handball coaches over one season.

2. Trial Methods

2.1 Trial Design

The evaluation follows the MRC framework for complex interventions (17). The study is conducted by a parallel two-armed, pragmatic, superiority cluster-RCTs. Clubs are randomised to either the control group that continue their activity as normal or the intervention group participating in #Utviklingsklar. #Utviklingsklar includes a digital e-learning course, an in-person workshop, and a club meeting, all three activities involving participation of one club leader and a minimum of one coach from each participating team within each club.

2.2 Randomisation

Upon enrolment, clubs will be randomly assigned to either the control or intervention group in a 1:1 allocation ratio, using a computer-generated cluster randomisation schedule, taking differences in cluster size into account and stratified by geographical region. The biostatistician responsible for the randomisation and primary statistical analysis will be blinded to group allocation. It is impossible to blind players, coaches, and clubs to group allocation. For practical reasons (i.e., data monitoring and participant follow-up), neither the PhD students nor the principal investigator will be blinded.

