4.1 Screening Data, Eligibility and Recruitment

Clubs will be eligible for participation if they are able to participate with one club leader, 2-6 teams (teams from at least two different age groups (13-17) and both the boy and girl league should ideally be represented), and a minimum of one coach from each of the participating teams.

A CONSORT flow diagram (18) will be used to summarize the number of participants who were:

- Included and randomised
- Received the intervention
- Lost to follow-up (reasons will be provided)
- Randomised and included in the primary analysis

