5.2.1 Primary Outcome

Analysis

The primary outcome (weekly injury severity score) will be analyzed with a linear mixed model. The model will include fixed effects for intervention (intervention vs control), time point, intervention x time point interaction, and geographical region (stratification factor in the randomisation). Time point is defined as 1 for the first response to the OSTRC questionnaire (week 42, 2024), 2 for the second response to the questionnaire (week 44, 2024), and so on until 13 for the last response (week 14, 2025). The model will include random intercepts for players nested within clubs. The predicted margins over all time points will be presented for intervention and control separately with 95% confidence intervals (CIs). The effect measure will be the difference between the weekly injury severity score for intervention and control, estimated as the predicted marginal effect of intervention over all time points, based on the fitted linear mixed model. The effect estimate will be presented with a 95% CI and a P-value for the null hypothesis of a difference equal to zero.

The predicted margins for intervention and control will be presented with 95% CIs for each time point in a plot. The estimated intervention effect (difference between intervention and control) with a 95% CI for each time point will also be shown in a plot.

Assumption checks

The distribution of the primary outcome (injury severity score) will be assessed with descriptive statistics and histograms. With a sample size of approximately 2000, the linear mixed model will be robust to quite large deviations from the normal distribution, and the injury severity score is bounded below at 0 and above at 100, so its distribution cannot be severely skewed. Still, in the unlikely case that the distribution of the outcome is deemed to deviate too much from the normal distribution, a log transformation of the outcome will be done prior to fitting the linear mixed model. In that case, an analysis of the untransformed data will be performed as an additional sensitivity analysis. After fitting the model (original scale or log transformed), plots of observed and model-fitted values (by intervention group and time point) will be compared to assess the fit of the model.

Missing data

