5.2.3 Continuous Secondary Outcomes Measured at a Single Time Point

Analysis

Injury burden is a single-measure continuous outcome, and the unit of analysis is team. It will be analyzed with a linear regression model with intervention (intervention vs control), geographical region (stratification factor in the randomisation), and number of players per team (due to potential large variation between teams) as the explanatory variables. The standard errors will be adjusted to account for clustering within clubs. Based on the fitted model, the predicted margins for intervention and control separately and the predicted marginal effect of intervention will be presented with 95% CIs.

Assumption checks

The distribution of the residuals from the fitted linear regression model will be assessed with descriptive statistics and histograms. If the distribution of the outcome is deemed to deviate too much from the normal distribution, median regression with bootstrap confidence intervals will be used instead of linear regression. Medians and differences of medians will be reported instead of means and differences in means.

Missing data

STATISTICAL ANALYSIS PLAN for Effectiveness of the Injury-preventive Program #Utviklingsklar

Since the analysis of burden will be performed on teams as the unit of analysis, we do not expect that there are teams with missing data on burden, which would indicate that there are no data on severity score and/or exposure for any players in the team.

In cases where data are missing between two consecutive reports of the same injury, values from the preceding report should be carried forward. Consecutive reports with identical classifications for Acute/Overuse, Body Area, and Activity are considered the same injury and the incidence ID assigned to the earliest report in the sequence will be carried forward on the preceding injuries.

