5.2.5 Ordinal Secondary Outcomes

Analysis

STATISTICAL ANALYSIS PLAN for Effectiveness of the Injury-preventive Program #Utviklingsklar

The ordinal secondary outcomes on coach practices are measured as the change in an ordinal 7-point scale from baseline to end of season. The change (baseline minus end of season) will be an outcome ranging from -6 (score 1 at baseline and 7 at end of season) to 6 (score 7 at baseline and 1 at end of season). This outcome is an ordinal outcome with 13 categories. With approximately 120 coaches, many of the categories will be sparsely populated, and we believe that an ordinal regression model would be a poor choice with these many categories and so few data. Instead, we will compare the mean number of categories of change from baseline to end of season for intervention vs. control. The outcomes will be analyzed with linear regression models with intervention (intervention vs control) and geographical region (stratification factor in the randomisation) as the explanatory variables. The standard errors will be adjusted to account for clustering within clubs. Based on the fitted model, the predicted margins for intervention and control separately and the predicted marginal effect of intervention will be presented with 95% CIs. The observed counts (and percentages) on the original 13-point ordinal scale will be presented for intervention and control.

Assumption checks

The distributions of the residuals from the fitted linear regression models will be assessed with descriptive statistics and histograms. With only 13 possible outcomes, it is very unlikely that the distribution of the residuals will exhibit any signs of large deviations from the normal distributions. Still, in the case that the distribution of the outcome is deemed to deviate too much from the normal distribution, a log transformation of the outcome will be done prior to fitting the model.

Missing data

The main analysis of the ordinal secondary outcomes will be performed on the complete case sample. As a sensitivity analysis, we will impute missing data with multiple imputation. The imputation model will be multinomial logistic regression, stratified by intervention/control, and it will include the following explanatory variables:

- Age level (team)
- Sex (team)
- Education in injury diagnosis/treatment/prevention (coach)
- Access to health personnel (team)
- Coaching experience (coach)
- University-level coaching education (coach)

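### Club allocation takes cluster size into account as well as region, but the primary, secondary severity and coach models adjust for region only: a cheap precision gain is left unused

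*SAP*

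**What the plan says.** The handball SAP and the football SAP use the same wording on each item below.

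- **Allocation (2.2).** Clubs are randomised "in a 1:1 allocation ratio", "taking differences in cluster size into account and stratified by geographical region". Two features of the clubs are named. How size was used (strata, ordered blocks, minimisation, a constraint on arm totals) is not stated.
- **Eligibility (4.1).** A club may enter "2-6 teams (teams from at least two different age groups (13-17"), so the number of participating teams can vary threefold.
- **Primary model (5.2.1).** It has "fixed effects for intervention (intervention vs control), time point, intervention x time point interaction, and geographical region (stratification factor in the randomisation"). On clustering: "The model will include random intercepts for players nested within clubs". Section 5.2.2 analyses the secondary severity outcomes in the same way.
- **Coach models.** Section 5.2.4 uses the same fixed effects as the primary model. Section 5.2.5 uses "linear regression models with intervention (intervention vs control) and geographical region (stratification factor in the randomisation) as the explanatory variables", with standard errors clustered on club.
- **Burden model (5.2.3).** Besides intervention and region it has "number of players per team (due to potential large variation between teams) as the explanatory variables". This is a team-level measure, justified by variation between teams and not by the allocation.

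**The concern.** Each model includes region with the stated reason that it is the "geographical region (stratification factor in the randomisation"). The same reasoning points to the other feature used in the allocation, yet cluster size appears in none of the primary, secondary severity or coach models.

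Suppose size restricted the allocation and is related to outcome. The design has then removed the size-related differences between clubs from the arm comparison, but a model without size still counts them as between-club variance. The random club intercept does not cure this: it keeps that variance in the standard error. Club-clustered standard errors behave the same way, because the size effect stays in the residuals. Intervals come out wider than they need to be, in a trial whose precision rests on 26 to 30 clubs.

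**Working it through.** **Inputs from section 2.3 of both SAPs:** difference 8.5 (34 against 25.5), SD 30, ICC 0.05 or less, 64 players per club, 13 clubs per arm needed, 15 targeted, 80% power, two-sided alpha 0.05.

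**The plan's own figure.** Without clustering, n per arm = 2 × (30 × (1.960 + 0.842)/8.5)² = 195.5, so 196. The design effect is 1 + 63 × 0.05 = 4.15. Clubs per arm = 196 × 4.15/64 = 12.7, rounded up to 13. The stated 13 reproduces.

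**Share of a club mean's variance that lies between clubs.** Between-club variance = 0.05 × 900 = 45. Within-club variance = 855. Variance of a club mean = 45 + 855/64 = 58.36. Share λ = 45/58.36 = 0.771.

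**Effect of omitting a balanced size factor.** Let R² be the share of the between-club variance that size explains, with size fully balanced between arms. R² is an assumption, because the documents give no value.

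- Model SE / true SE = 1/√(1 − R² × λ)
- Actual alpha = 2 × (1 − Φ(1.96/√(1 − R² × λ)))

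| Assumed R² | SE too large by | Actual alpha (normal approximation) |
|---|---|---|
| 0 | 0% | 0.050 |
| 0.05 | 2% | 0.046 |
| 0.10 | 4% | 0.041 |
| 0.30 | 14% | 0.025 |

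**Simulation check.** A club-level simulation (20,000 runs, 13 clubs per arm, two size groups, t reference) gave these results without and with the size term:

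| Assumed R² | Mean CI width | Type I error |
|---|---|---|
| 0 | 12.2 vs 12.3 | 0.050 vs 0.051 |
| 0.10 | 12.3 vs 11.8 | 0.044 vs 0.051 |
| 0.25 | 12.4 vs 11.1 | 0.030 vs 0.049 |

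The width ratios, 12.3/11.8 = 1.04 and 12.4/11.1 = 1.12, agree with the formula (4% at 0.10; 11% at 0.25).

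**Power.** The model SE at 13 clubs per arm is √(2 × 58.36/13) = 3.00. The true SE is 3.00 × √(1 − R² × λ), which is 2.88 at R² = 0.10 and 2.63 at R² = 0.30.

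- Without the size term, power = Φ((8.5 − 1.96 × 3.00)/true SE): 81% at R² = 0, 82% at 0.10, 84% at 0.30.
- With it, power = Φ(8.5/true SE − 1.96): 81%, 84% and 90%.

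So the omission forgoes about 2 and 6 points in the last two cases, and power never falls below the 81% the design gives without any size effect.

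**Lower ICC.** At an assumed ICC of 0.01, λ = 9/(9 + 891/64) = 0.39. R² = 0.10 then gives an SE 2% too large, and R² = 0.30 gives 6% to 7%.

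**Coach models.** About 120 coaches (5.2.5) over 30 clubs is 4 per club. At an assumed ICC of 0.05, λ = 0.05/(0.05 + 0.95/4) = 0.17. The SE is then about 1% too large at R² = 0.10 and 3% at R² = 0.30. Even this is generous for 5.2.4: its effect is a difference of changes within coach, from which a size effect that is constant over time largely cancels.

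**The case against.** The strongest reply is that the premise is inferred. Section 2.2 does not say that clubs were balanced on size. Only region is called a stratification factor, so the label in the models is consistent with 2.2. Different methods would give different degrees of balance and call for different terms. **This stands**, and it is why the first step is to state the method.

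The harm also depends on an undocumented link. Nothing in either SAP relates the number of players or teams a club enters to injury severity. **This stands.** If there is no link, the omission costs nothing.

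The figures for the primary model are near an upper bound. They take the ICC at the top of the stated range and assume full balance. With about 30 clubs already divided by region, balance will be approximate, and any size variation shared with region is already adjusted for. **This stands.**

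Stronger readings are tempting, but the documents do not support them:

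- A reader might infer that the primary result is biased or that its type I error is inflated. Omitting a balanced factor from a linear model does neither; the error is on the conservative side.
- A reader might infer that the trial is underpowered. The 13 clubs per arm reproduces and is unaffected.
- A reader might take the burden model as evidence that the plan already treats club size as relevant. Players per team is not club size, and the reason given for it is not the allocation.
- A reader might carry the 77% between-club share over to the coach models. It rests on 64 players per club and does not apply with about 4 coaches per club.

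What survives is the mismatch in the text, and a remedy that costs almost nothing.

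**Conclusion.** The point holds as a minor one. Both SAPs name cluster size and region in the allocation and carry only region into the primary, secondary severity and coach models, without explanation. For the primary outcome the possible cost is a standard error at most about 2%, 4% or 14% too large, for assumed shares of 5%, 10% or 30%. This rests on three assumptions: size restricted the allocation and ended up balanced, the ICC is 0.05 with 64 players per club, and size predicts severity to the stated degree. The cost shrinks as any of these weakens and is nil if size is unrelated to outcome. In the coach models, which are supportive only, it is about 1% to 3%.

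**What to change.** In section 2.2 of both SAPs, state how cluster size entered the allocation: which measure, which categories if any, and by what method. Then add that same club-size variable, in the form used and as fixed at randomisation (not a later count of responders), as a fixed effect next to region in the primary model (5.2.1). For consistency, do the same in the secondary severity (5.2.2), burden (5.2.3) and coach models (5.2.4, 5.2.5), and describe region and club size together as the factors used in the randomisation. In the burden model, players per team does not replace it. If size turns out not to have restricted the allocation, say so and justify leaving it out.

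The cost is wording, one covariate that is already known, and about one club-level degree of freedom out of 24 to 28 (26 to 30 clubs less 2, before region terms), or more if size has several categories. The sample size does not change.

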2.3 Sample size

Sample size calculation has been based on the primary endpoint (using player average weekly injury severity score during the study period of one season). Sample size estimations under varying assumptions for cluster size and effect were performed by the project biostatistician. Data from one previous study in the target population were used to estimate the average weekly injury severity score in the control group and expected standard deviation. Assuming club sizes of 64 players, 13 clubs in each trial arm are sufficient to detect a difference between the average weekly injury severity score of 34 (intervention group) and 25.5 (control group), with a pooled standard deviation of 30, 80% power, 2-tailed alpha of 0.05, and an ICC of 0.05 or less. This corresponds to a relative reduction of 25%. We will overshoot recruitment by four clubs to allow for potential withdrawal of clusters. The target number of clubs to recruit is therefore 15 in each trial arm. As cluster sizes are large, the risk of type II errors due to individual participant data loss is minor.

